## 8 General Analysis Considerations

### 8.1 Timing of Analyses

The final analyses of the clinical trial will be performed after

- 1) All enrolled participants either (a) completed 18 months of follow-up from enrollment or (b) discontinued early from the study.
- 2) Any chart reviews or investigations needed to confirm dates of elements of the primary composite endpoint were identified and completed.
- 3) All study data were entered, locked and unblinded as per SABER SOPs.

This SAP document was finalized and approved prior to the double-blind database lock and unblinding.

### 8.2 Analysis Populations

#### 8.2.1 Modified Intention to Treat Population

The main population for efficacy is the modified intention-to-treat population (m-ITT), defined as all participants randomized, receiving at least one dose of study medication, and having at least one post-baseline efficacy assessment. Subjects were analyzed by assigned treatment.

#### 8.2.2 Per Protocol Population

The Per Protocol (PP) analysis set consists of all participants in the m-ITT population who completed 18 months of study medication (i.e., both MMF and PFD/Plac) and do not have a major protocol violation, defined as violation of entry criteria or taking prohibited medications. The study window for month 18 visit is  $\pm$  6 weeks. Membership in the PP analysis population was determined before study unblinding.

#### 8.2.3 Completers Population

The Completers analysis set consists of all subjects in the m-ITT population who had an 18-month efficacy outcome (regardless of completion of study medication). It can be different depending on the outcome that is analyzed.

#### 8.2.4 Safety Population

The Safety Population is defined as all participants who were randomized and received at least one dose of the study medication. The Safety Population was used for all safety analyses. Subjects were analyzed by assigned treatment.

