6.1.2 Study Agent Formulation, Appearance, Packaging and Labeling

All study agents used in this protocol will be provided in sealed and clearly identified bottles from their respective manufacturers and stored by the UCLA Pharmacy Core for distribution to the participating clinical site research pharmacies without modification or relabeling.

On-site, at the Clinical Site Research Pharmacy, patient specific labeling will be added to the existing MMF bottles when supplied as 500 capsule bottles from the manufacturer. Alternatively, when supplied as 100 capsule bottles, bottles derived from the same lot will be transferred at the time of dispensing into a single generic bottle to produce bottles of 500 capsule each. In such cases, labels containing both drug information and patient specific identification and instructions will be applied. Use of existing bottles is not a concern for this study drug as it will be provided in an open-label format to study participants. However, in order to maintain the blind and avoid disclosure due to the manufacturer labeling, capsules from individual bottles of PFD and Plac must be transferred at the time of prescription into new generic bottles and fresh labels attached by the site pharmacy. In addition to patient specific labeling information, the information from the study label will be replicated except that the contents will indicate capsules that contain either "267 mg of PFD or matching Plac".

6.1.2.1 **Mycophenolate Mofetil (MMF)**

Formulation and strength: Size 1 hard opaque gelatin capsules containing 250 mg

Appearance: Opaque capsules, Blue and Orange

(Teva example, coloring will vary by manufacturer)

Packaging: Supplied in Bottles of either 100 capsules (NDC 0093-7334-01) or 500 capsules (NDC 0093-7334-05) with barcodes and labels

(Teva example, labeling will vary by manufacturer)

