10.3 ANALYSIS DATASETS

Several analysis sets will be used in analyses:

- The main population for efficacy will be the modified intention-to-treat population (m-ITT), defined as all participants randomized, receiving at least one dose of study medication, and having at least one post-baseline efficacy assessment. Subjects will be analyzed by assigned treatment.
- A second analysis set will be used to assess the robustness of the primary and key secondary conclusions in the subset of participants in the m-ITT analysis set who complied with the protocol sufficiently to ensure that these data would be likely to represent the effect of treatment according to the underlying scientific model. The Per Protocol (PP) analysis set will consist of all subjects in the m-ITT population who do not have a major protocol violation, inclusive of violation of entry criteria.
- The Safety Population is defined as all participants who are randomized and receive at least one dose of the study medication. The Safety Population will be used for all safety analyses. Subjects will be analyzed by assigned treatment.

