#### 5.1.2 Secondary Objective

To demonstrate that combination therapy with PFD and MMF is well tolerated, in comparison to MMF alone, and not associated with limiting toxicity that impacts on the overall treatment effect.

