## 11 Safety Analyses

Safety data, including AEs, clinical laboratory tests, vital signs, physical examinations, and concomitant medication usage will be summarized descriptively overall and by treatment group for the Safety Population. AEs include frequency of events and/or incidence of study subjects experiencing events, by study arm for the following:

- a) Study-defined treatment failures
- b) Study-defined treatment emergent AEs of special Interest
- c) All treatment-emergent AEs, total and by organ system classification
- d) All treatment-emergent AEs related to study medication, total and by organ system classification
- e) All treatment-emergent SAEs, total and by organ system classification
- f) All treatment-emergent SAEs related to study medication, total and by organ system classification
- g) All treatment-emergent AEs and SAEs that result in discontinuation of study medication
- h) Time to treatment failure
- i) Time to treatment-emergent AEs and SAEs resulting in premature discontinuation of study medication

For categorical safety outcomes, numbers and percentages will be used. For continuous safety outcomes, number, mean, standard deviation, median, interquartile range, minimum and maximum are used to summarize changes from baseline to each study visit in laboratory tests and vital signs. Percent change from baseline for laboratory values are summarized. The primary organ system associated with each adverse event was coded by the medical monitor. Kaplan-Meier methods are used to summarize graphically the time to treatment failure, and treatment-emergent AEs and SAEs that result in premature discontinuation of study medication.

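### Safety is grouped by assigned treatment, so adverse events of any participant given the other arm's capsules would be counted in the wrong arm

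*SAP*

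**What the plan says.** The two documents agree. SAP 8.2.4 admits "all participants who were randomized and received at least one dose of the study medication", applies this set to every safety analysis, and continues: "Subjects were analyzed by assigned treatment". Protocol 10.3 has the same rule in the future tense: "The Safety Population will be used for all safety analyses. Subjects will be analyzed by assigned treatment".

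SAP section 11 applies this set to adverse events, laboratory tests, vital signs, physical examinations and concomitant medication, which "will be summarized descriptively overall and by treatment group for the Safety Population". Tolerability is the stated secondary objective in SAP 5.1.2: "To demonstrate that combination therapy with PFD and MMF is well tolerated, in comparison to MMF alone".

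On supply, Protocol 6.1.2 says that "capsules from individual bottles of PFD and Plac must be transferred at the time of prescription into new generic bottles", with a fresh label attached by the site pharmacy. This keeps the blind, because the manufacturer's bottles show their contents.

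Neither document says how to handle a participant who took the other arm's capsules or a mixture. The list of changes in SAP section 14 leaves the rule alone.

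**The concern.** Membership of the safety set depends on exposure, but its arms depend on randomization. For efficacy, grouping by assignment protects the randomized comparison, and any crossover of capsules dilutes the effect that the trial hopes to show. For safety the same dilution works the other way. If PFD raises the rate of an event, counting a PFD-exposed participant under placebo, or the reverse, narrows the expected difference and so favours a finding of good tolerability.

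The site-level transfer into generic bottles makes a wrong-capsule error possible. Only the attribution between PFD and placebo is at stake, since both arms take open-label MMF. Nothing else in the SAP regroups such events. The Per Protocol set removes participants unless they "do not have a major protocol violation, defined as violation of entry criteria or taking prohibited medications", and a dispensing error is not named there. SAP 9.2 would summarise a known error as a deviation, but its events would stay in the assigned arm.

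**Working it through.** The plan states no figure that depends on this rule, so there is nothing to reproduce. The arithmetic only shows how large the effect could be.

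**Inputs**
- Number of participants: 51, from the index range of the primary model in SAP 10.1. That model uses the m-ITT set. The Safety Population does not require a post-baseline efficacy assessment, so it could be larger; its size is not stated.
- Split: 26 PFD and 25 placebo, assumed from 1:1 randomization (SAP 6.3).
- Event rates: nausea 36% on PFD and 16% on placebo, from the IPF trials in Protocol Table 2.3.1.2.4a, assumed to apply here.

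**Ceiling for one participant.** One participant is 1/26 = 3.8% or 1/25 = 4.0% of an arm. An arm's incidence can therefore move by at most about 4 points. Regrouping takes the participant out of one arm and puts them in the other, so in the extreme case both incidences move. For example, a PFD-assigned participant who took placebo has the only event. By assignment this gives 1/26 versus 0/25, a difference of +3.8 points. By treatment received it gives 0/25 versus 1/26, a difference of −3.8 points.

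**Expected effect when k participants take the wrong capsules throughout.** The true difference is 36 − 16 = 20.0 points.
- k PFD-assigned took placebo: [(26 − k) × 36 + k × 16]/26 − 16. For k = 1, 916/26 − 16 = 35.23 − 16 = 19.2.
- k placebo-assigned took PFD: 36 − [(25 − k) × 16 + k × 36]/25. For k = 1, 36 − 420/25 = 36 − 16.8 = 19.2.

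| Wrongly treated throughout | Expected difference by assignment |
|---|---|
| 0 | 20.0 |
| 1 | 19.2 |
| 2, same direction | 18.4 to 18.5 |
| 3, same direction | 17.6 to 17.7 |
| 1 in each arm | 18.4 |

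Grouping by treatment received restores 20.0 in every row.

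**Less common events.** Protocol 2.3.1.2.3 gives IPF rates on PFD of 9% for photosensitivity and 3.7% for ALT or AST at or above 3 times the upper limit. In an arm of 25, if these apply, the expected counts are 25 × 0.09 = 2.25 and 25 × 0.037 = 0.9. With counts this low, one misplaced case can change how a table reads, although the expected bias is small.

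**A single slip.** The dispensing visits in SAP 6.4 are 28 to 84 days apart over 504 days. One wrong dispensing therefore covers 28/504 = 6% to 84/504 = 17% of the dosing period. Wrong treatment throughout would need the same error to be repeated, or the assignment itself to be misread.

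**The case against.** The strongest reply is that this is a consistent, pre-specified choice whose consequence is hypothetical. No misdispensing is reported, and the supply chain has several checks. The site pharmacy logs every bottle, date, capsule count and recipient (Protocol 6.2.2). The site team logs bottle IDs and keeps used bottles for the monitor (6.2.3). The DCC reconciles the three inventories (6.2.4), and the clinical monitor checks accountability (section 9). A known error would be a protocol deviation, summarised by arm under SAP 9.2 and listed if classed as major. Safety is descriptive, so no planned test depends on the grouping. All of this stands. It makes the point minor, but it does not show that the rule would put events in the right arm if an error did occur.

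Two further points also stand. The 4-point figure is a ceiling for an arm's incidence, not an expected bias, and a single slip gives only partial exposure. The logs are not infallible either: an unnoticed wrong transfer may be recorded as correct. The participant-level inventory in Protocol 7.1.1.10 gives type only as MMF versus PFD/Plac, so the arm has to be traced through lot and bottle numbers.

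A reader might infer that safety results are already misattributed, that the two documents conflict, or that any PFD dose should place a participant in the PFD arm. The documents report no error, and they state the same rule. A rule based on any PFD dose would charge a placebo participant's whole follow-up to PFD after one wrong bottle, although 83% or more of the dosing period (100% − 17%) was on placebo. That repeats the misattribution on a larger scale.

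**Conclusion.** The point holds as a minor, low-cost improvement. Under SAP 8.2.4 and Protocol 10.3, events of a participant who took the other arm's capsules would be counted in the wrong arm. The expected bias is toward no difference between PFD and placebo, which is not conservative for the tolerability objective.

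Its size is conditional. It is zero if no error occurred. Otherwise, for one participant wrongly treated throughout, it is at most about 4 points on an arm's incidence, with an expected shrinkage of about 0.8 point. These figures rest on about 25 per arm, which is assumed because the Safety Population size is not given, and on IPF nausea rates carried over to this population.

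**What to change.** In SAP 8.2.4, group safety analyses by the PFD/placebo treatment actually received, taken from the reconciled pharmacy bottle logs. Then:

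- Classify a participant with mixed exposure by the treatment received for most of the dosing period, not by any single PFD dose.
- List every participant whose received and assigned treatments differ, with the dates and duration of the discordant exposure and the events during it. After a single slip the participant would stay in the assigned arm, so this listing is what shows the affected events.
- State the number of such participants even if it is zero. That closes the question.
- Keep assigned treatment for the m-ITT set.
- Record the change in SAP section 14, because it departs from Protocol 10.3.

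The cost is a few sentences in the SAP, one listing, and tracing bottles to lots in logs that already exist. Results do not change if there was no error. An error that was logged as correct would remain undetected.

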### 8.3 Covariates and Subgroups

Prior MMF therapy (stratification factor: naïve,  $>0$  to  $\leq 3$  months, and  $>3$  months to 6 months) and FVC-% at baseline were included as covariates in the analysis of the primary efficacy endpoint. Several other covariates are incorporated in specific analyses that are denoted in the analysis specifications described below (e.g., secondary analysis of primary endpoint including baseline mRSS as a covariate). No subgroup analyses were planned.

## 8.4 Missing Data

Our primary analytic approach assumes a missing-at-random mechanism^8. Sensitivity analyses are performed to assess how subjects who withdrew might affect conclusions of the analysis for the primary endpoint.

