Sensitivity analyses will be performed to assess how subjects who withdrew may affect conclusions of the analysis. In particular, our primary analytic approach assumes a missing-at-random mechanism (45) and one sensitivity analysis will employ a nonignorable model. With nonignorable missingness, the stochastic process that generates missingness is explicitly modeled. We will jointly model the longitudinal measures with the missing data mechanism using a pattern mixture model (31). Depending on the extent and pattern of missingness, other simpler sensitivity analyses may be used: for example, change from baseline to the end of treatment for subjects completing the study

(completers) may be analyzed using an analysis of variance model. The model will include the same covariates that are included in the primary mixed effects analysis.

In addition to the assessment of the overall trajectory of pulmonary response which integrates the timing of the onset of response and the overall magnitude of effect at 18 months, we will evaluate the individual components of this response. Using the same model as for the primary endpoint, we will assess the change point for response to evaluate the onset of response for the two treatment groups, and the change from baseline to month 18 to evaluate the overall magnitude of effect at the end of the treatment period.

In addition, frequency distributions of changes from baseline to 18 months in FVC-% will be presented by treatment group to describe observed (i.e., not model-based) estimates of treatment effects for the m-ITT analysis set, for those who completed 18 months of treatment and those who prematurely discontinued treatment. Additional analyses may be performed to assess more granular changes in treatment adherence (e.g., premature discontinuation of study treatment prior to 3, 6, 9, 12, 15 and 18 months) depending upon the observed extent and timing of discontinuation.

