## 10.2 Secondary Efficacy Analyses

### 10.2.1 Secondary Analyses of Primary Efficacy Endpoint

Several sensitivity analyses are performed to assess how alternative approaches to missing data and model assumptions affect the conclusions of the analysis of the primary outcome:

1. Analysis of the primary efficacy variable as described in section 10.1 is performed using the PP population.
2. Analysis of the primary efficacy variable described in section 10.1 with the m-ITT analysis set except that HRCT fibrosis scores in the lobe of maximal involvement (QLF-LM) at screening is added as a covariate.
3. Analysis of the primary efficacy variable described in section 10.1 with the m-ITT analysis set except that baseline mRSS is added as a covariate.
4. Analysis of covariance (ANCOVA) is used to analyze the change of FVC-% from baseline to month 18 (that is, FVC-% at month 18 - FVC-% at baseline). The model includes the treatment group, baseline FVC-% and prior MMF therapy.
5. In addition to the assessment of the overall trajectory of pulmonary response which integrates the timing of the onset of response and the overall magnitude of effect at 18 months, we evaluate the individual components of this response. This is accomplished by using the linear mixed effects model with same covariates described for the analysis of primary efficacy variable and provide adjusted estimates of change from baseline in FVC-% for each treatment group and treatment difference for each time point (e.g., 3, 6, 9, 12, 15 and 18 months).
6. Descriptive statistics are provided to assess more granular changes in FVC-% by treatment adherence (e.g., premature discontinuation of study treatment prior to 3, 6, 9, 12, 15 and 18 months) in the completers population.

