##### e. Add Completers Population

Add Completers analysis set that wasn't in the protocol to provide an analysis population for descriptive statistics of select efficacy endpoints.

PROTOCOL:

N/A

SAP:

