**g. Remove One of Analysis of the Primary Efficacy Endpoint**

Because we had to stop enrollment before the planned sample size was achieved, we don't have sufficient data to perform the analysis to access the change point for response.

PROTOCOL:

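### The SAP omits the protocol's non-ignorable (pattern-mixture) sensitivity analysis without recording it, so no listed analysis of the primary endpoint tests a departure from missing-at-random

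*SAP*

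**What the plan says.** Protocol 10.4.2 assumes MAR for the primary analysis and then states that "one sensitivity analysis will employ a nonignorable model". It names the method: "We will jointly model the longitudinal measures with the missing data mechanism using a pattern mixture model". Simpler analyses, such as one of completers, are permitted as further options.

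SAP 8.4 repeats the MAR assumption and says "Sensitivity analyses are performed to assess how subjects who withdrew might affect conclusions of the analysis for the primary endpoint", without naming a method. SAP 10.2.1 opens with "Several sensitivity analyses are performed to assess how alternative approaches to missing data and model assumptions affect the conclusions" and lists six items:

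1. the primary model in the per-protocol (PP) set;
2. the primary model plus screening QLF-LM;
3. the primary model plus baseline mRSS;
4. an ANCOVA of the month-18 change;
5. by-visit estimates from the mixed model;
6. descriptive FVC-% by timing of discontinuation, in completers.

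The PP definition also differs between the documents. Protocol 10.3 says "The Per Protocol (PP) analysis set will consist of all subjects in the m-ITT population who do not have a major protocol violation". SAP 8.2.2 restricts the set to those "who completed 18 months of study medication (i.e., both MMF and PFD/Plac) and do not have a major protocol violation".

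SAP Section 14 records nine changes, items a to i. Item g, "Remove One of Analysis of the Primary Efficacy Endpoint", covers the change-point analysis from Protocol 10.4.2. Item e is "Add Completers Population". No item mentions the pattern-mixture analysis or the new PP definition.

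**The concern.** The primary result rests on MAR, and much of the follow-up makes that reasonable. Treatment failure is triggered by recorded FVC-% (Protocol 5.3.2). Participants who stop only PFD/Plac keep all visits (Protocol 5.3.3). Follow-up continued after stopping drug unless consent was withdrawn (SAP 6.1).

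What no model can verify is the FVC-% of those who withdrew or did not come back. The tables by treatment status in SAP 10.2.2 (items 8 to 10) are descriptive and cover only participants with a month-18 value. If unseen participants in one arm did worse than their earlier visits predict, the estimated difference is biased, and no planned analysis shows how much of this the conclusion would survive. The protocol had pre-specified a check for exactly that.

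**Working it through.** **Comparison of the texts**

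- Items 2, 3 and 5 of SAP 10.2.1 are MAR likelihood models with an added covariate or by-visit output.
- Item 4 uses observed month-18 values only. It needs a stronger assumption than the mixed model, not a weaker one.
- Item 1 uses a PP set that now excludes everyone who stopped either drug and nearly all treatment failures (one confirmed only at month 18 could remain). It cannot show the effect of withdrawals.
- Item 6 is descriptive and limited to participants with a month-18 value.

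Count: 0 of 6 analyses allow missing-not-at-random, and 0 of 9 change-log items record the omission.

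**The plan's own missing-data figure**

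SAP Table 7.1 gives cumulative dropout of 6.5, 13, 17, 20, 23 and 24% at months 3 to 18. Mean retention is 1 − (0.065 + 0.13 + 0.17 + 0.20 + 0.23 + 0.24)/6 = 0.8275, which agrees with the stated 83%. N at month 18 is 75 × 0.76 = 57, as tabulated.

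**Missing share within m-ITT**

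The m-ITT set needs one post-baseline assessment (SAP 8.2.1). If those lost by month 3 have none, the share becomes (d − 6.5)/93.5 = 0, 7.0, 11.2, 14.4, 17.6 and 18.7%.

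**Month-18 difference**

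Let δ be the assumed number of points by which unseen PFD-arm values fall below the MAR prediction, relative to control. The loss is δ × 0.24 (all randomised) or δ × 0.187 (m-ITT).

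| δ | All randomised | m-ITT |
|---|---|---|
| 2.5 | 0.60 | 0.47 |
| 5 | 1.20 | 0.94 |
| 10 | 2.40 | 1.87 |

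- At δ = 5, Scenario 1 (2.5 points) loses 1.20/2.5 = 48% or 0.94/2.5 = 37%. Scenario 2 (3.25 points) loses 37% or 29%.
- Erasing Scenario 1 needs δ = 2.5/0.24 = 10.4 or 2.5/0.187 = 13.4.

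**Treatment-by-month slope**

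SAP 10.1 names this parameter. Fit a least-squares line to the planned differences; the centred sum of squares of the months is 157.5.

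- Scenario 1: (7.5 × 2.0 + 4.5 × 1.125 + 1.5 × 0.25)/157.5 = 20.44/157.5 = 0.130 points per month.
- Dropout share, all randomised: (7.5 × 0.175 + 4.5 × 0.10 + 1.5 × 0.03)/157.5 = 0.0115 per unit δ. For m-ITT: 0.0115/0.935 = 0.0123.
- At δ = 5 the loss is 0.057 (44%) or 0.061 (47%).
- Scenario 2: (7.5 × 2.5 + 4.5 × 1.5 + 1.5 × 0.125)/157.5 = 0.163, so the same shift costs 35% or 38%.

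**At the reduced sample**

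The model in SAP 10.1 indexes 51 patients. Assume 26 versus 25 per arm, the Table 7.1 SDs and correlations, and the planned monotone dropout. About 5 to 6 PFD participants are then unseen at month 18 (26 × 0.187 = 4.9; 26 × 0.24 = 6.2). The likelihood information gives these values for the month-18 difference:

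| | All randomised | m-ITT |
|---|---|---|
| Standard error | 1.86 | 1.80 |
| 1.96 × SE | 3.65 | 3.53 |
| Plus the δ = 5 loss | 4.85 | 4.47 |

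An estimate between about 3.5–3.7 and 4.5–4.9 would be significant under MAR and lose significance at δ = 5. This holds the standard error fixed.

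**The case against.** The omission is inferred partly from silence. SAP 4.1 says the SAP is to be read together with the protocol, and the planned outputs are in a separate document. That does not put the analysis in the SAP's own list, and the SAP does not cite the protocol's pattern-mixture reference.

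The protocol foresaw simpler analyses, and the month-18 ANCOVA resembles its completers example. But those were optional, and the non-ignorable model was not. An observed-case analysis cannot test a departure from MAR.

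Requiring 18 months on drug may be a fair way to make the PP set represent adherent treatment. That stands: the definition can remain, and the defect is the missing log entry.

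On size, several points stand. Percentages against Scenario 2, which the SAP treats as the main case, are smaller. The remedy refits the m-ITT model, so the m-ITT figures match it best. A 13.4-point shift is 2.2 times the month-18 SD of 6.2, so complete erasure of the planned effect is remote. The significance window concerns a single-visit contrast (SAP 10.2.1 item 5), not the primary test, and at 51 participants the planned 2.5 points is non-significant even with no shift.

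The small sample could justify a simpler model. The SAP gives that reason for other removals but not for this one.

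**Conclusion.** The concern holds and should be fixed. A firm protocol commitment has no counterpart in the SAP's list, its removal is unrecorded, and nothing in the list replaces it. The primary analysis itself is not shown to be wrong.

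The possible effect is moderate: at an assumed 5-point one-sided shift and the planned dropout, 37 to 48% of the Scenario 1 month-18 difference and 44 to 47% of its slope. These figures depend on shifts that are assumptions and on planned, not actual, missingness. At 10% missing, the same shift costs 5 × 0.10 = 0.5 points. Equal shifts with equal missingness in both arms cancel. A large tipping value would strengthen the trial's result.

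**What to change.** Add one item to SAP 10.2.1, a delta-adjusted pattern-mixture multiple imputation of the primary model:

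- Impute values after each participant's last observed visit under MAR within arm, then add δ. Vary δ separately for PFD and placebo over 0, −2.5, −5, −7.5 and −10.
- Impute intermittent gaps with δ = 0, including visits flagged as emergency restrictions under Protocol 17.4.3.
- Refit the SAP 10.1 model and combine by Rubin's rules. Report the difference, 95% CI and p-value at each grid point, and the δ at which the conclusion changes.
- Give imputation from the control-arm profile as support.

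In Section 14, record (i) that this replaces the protocol's pattern-mixture model because of the reduced sample, and (ii) the changed PP definition. Label the PP analysis as an adherence analysis, not a missing-data check. If the item is added after unblinding, say so.

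The cost is about a day of programming, one SAP item and two log entries. No new data are needed, and the primary model does not change.
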